#### *Laboratory*

5. Adequate hematologic function independent of transfusion and growth factor support for at least 7 days prior to Screening and randomization:

- a. Absolute neutrophil count  $\geq 1.0 \times 10^9/L$ .
- b. Platelet count  $> 50 \times 10^9/L$ .
6. Adequate hepatic and renal function defined as:
  - a. Serum aspartate transaminase (AST) or alanine transaminase (ALT)  $\leq 2.5$  x upper limit of normal (ULN).
  - b. Estimated Creatinine Clearance  $\geq 30$  mL/min (Cockcroft-Gault).
  - c. Bilirubin  $\leq 1.5$  x ULN (unless bilirubin rise is due to Gilbert's syndrome or of non-hepatic origin, such as hemolysis).

#### *Demographic*

7. Men and women  $\geq 18$  years of age.
8. Eastern Cooperative Oncology Group (ECOG) performance status of 0 to 2.

#### *Ethical/Other*

9. Willingness to receive all outpatient treatment, all laboratory monitoring, and all radiological evaluations at the institution that administers study drug for the entire study
10. Ability to provide written informed consent and to understand and comply with the requirements of the study
11. Female subjects who are of non-reproductive potential (ie, post-menopausal by history - no menses for  $\geq 1$  year; OR history of hysterectomy; OR history of bilateral tubal ligation; OR history of bilateral oophorectomy). Female subjects of childbearing potential must have a negative serum pregnancy test upon study entry.
12. Male and female subjects who agree to use highly effective methods of birth control (eg, condoms, implants, injectables, combined oral contraceptives, some intrauterine devices [IUDs], sexual abstinence, or sterilized partner) during the period of therapy and for 90 days after the last dose of ibrutinib/chlorambucil or obinutuzumab, and at least 18 months after the last obinutuzumab dose for female subjects.

#### **4.2. Exclusion Criteria**

To be enrolled in the study, potential subjects must meet NONE of the following exclusion criteria:

1. Any prior chemotherapy, radiotherapy, small molecule inhibitors including kinase inhibitors, and/or monoclonal antibody used for treatment of CLL or SLL
2. Evidence of CNS involvement with primary disease of CLL/SLL
3. History of other malignancies, except:
  - a. Malignancy treated with curative intent and with no known active disease present for  $\geq 3$  years before the first dose of study drug and felt to be at low risk for recurrence by treating physician.

- 
- b. Adequately treated non-melanoma skin cancer or lentigo maligna without evidence of disease.
  - c. Adequately treated carcinoma *in situ* without current evidence of disease.
  4. Uncontrolled autoimmune hemolytic anemia or idiopathic thrombocytopenic purpura, such as those subjects with a declining hemoglobin level or platelet count secondary to autoimmune destruction within the 4 weeks prior to first dose of study drug, or the need for daily prednisone  $\geq 20$  mg daily (or corticosteroid equivalent) to control the autoimmune disease.
  5. Known or suspected history of Richter's transformation.
  6. Concurrent administration of  $>20$  mg/day of prednisone within 7 days of randomization unless indicated for prophylaxis or management of allergic reactions (eg, contrast).
  7. Known hypersensitivity to one or more study drugs.
  8. Vaccinated with live, attenuated vaccines within 4 weeks of first dose of study drug.
  9. Any uncontrolled active systemic infection or an infection requiring systemic treatment that was completed  $\leq 7$  days before randomization.
  10. Known bleeding disorders (eg, von Willebrand's disease or hemophilia).
  11. History of stroke or intracranial hemorrhage within 6 months prior to enrollment.
  12. Known history of human immunodeficiency virus (HIV) or active with hepatitis B virus (HBV) or hepatitis C virus (HCV). Subjects who are positive for hepatitis B core antibody, hepatitis B surface antigen, or hepatitis C antibody must have a negative polymerase chain reaction (PCR) result before enrollment. Those who are PCR positive will be excluded.
  13. Major surgery within 4 weeks of first dose of study drug.
  14. Any life-threatening illness, medical condition, or organ system dysfunction that, in the investigator's opinion, could compromise the subject's safety or put the study outcomes at undue risk.
  15. Currently active, clinically significant cardiovascular disease, such as uncontrolled arrhythmia or Class 3 or 4 congestive heart failure as defined by the New York Heart Association Functional Classification; or a history of myocardial infarction, unstable angina, or acute coronary syndrome within 6 months prior to randomization.
  16. Unable to swallow capsules or malabsorption syndrome, disease significantly affecting gastrointestinal function, or resection of the stomach or small bowel, symptomatic inflammatory bowel disease or ulcerative colitis, or partial or complete bowel obstruction.
  17. Concomitant use of warfarin or other Vitamin K antagonists.
  18. Requires treatment with a strong cytochrome P450 (CYP) 3A inhibitor (see Appendix C).
  19. Lactating or pregnant.
  20. Unwilling or unable to participate in all required study evaluations and procedures.

21. Unable to understand the purpose and risks of the study and to provide a signed and dated informed consent form (ICF) and authorization to use protected health information (in accordance with national and local subject privacy regulations).

## 5. TREATMENT OF SUBJECTS

### 5.1. Treatment Allocation and Blinding

This is an open-label study and no blinding will occur; neither subjects nor investigators will be blinded to treatment.

Approximately 212 subjects will be randomized. Two randomization schemes will be generated: one for each geographic region (North America versus Rest of World). Under each scheme, randomization will be stratified according to:

- Eastern Cooperative Oncology Group (ECOG) performance status of 0-1 vs 2
- Cytogenetics - will be stratified into one of three categories
  - del 17p
  - del 11q without del 17p
  - others (neither del 17p nor del 11q)

The randomization code will be controlled through a centralized procedure. The primary efficacy evaluation will be performed by an IRC that will be blinded to study treatment information.

### 5.2. Study Treatment

In all cases, treatment will be administered up to the specified maximum number of cycles, or until disease progression, unacceptable toxicity, or the subject meets any criteria specified in Section 9.2, whichever occurs first.

#### 5.2.1. Arm A: Ibrutinib PO and Obinutuzumab IV

**Ibrutinib** will be given orally at a dose of 420 mg daily (3 capsules). There is no prospective limitation to the duration of ibrutinib therapy, and should be administered until progression or unacceptable toxicity.

The first dose of ibrutinib will be taken in the clinic, after which ibrutinib will be issued to the subject as an ongoing 28-day supply for home administration. On Day 1, ibrutinib will be given as soon as the subject comes into clinic. Pre-medications and obinutuzumab will then be given as outlined below.

**Obinutuzumab** will be administered intravenous at a fixed dose of 1000 mg over 6 cycles: given on Days 1+2 (100 mg on Day 1 and 900 mg on Day 2), Day 8 (1000 mg) and Day 15 (1000 mg) of Cycle 1 and on Day 1 (1000 mg) only of subsequent cycles, for up to 6 cycles.

Intravenous obinutuzumab will be administered per Section 5.3.2.3.

In the event of permanent discontinuation of concomitant obinutuzumab therapy, treatment with ibrutinib will continue as originally scheduled.

### **5.2.2. Arm B: Chlorambucil PO and Obinutuzumab IV for Six 28-day Cycles**

**Chlorambucil** will be administered orally at a dose of 0.5 mg/kg body weight, on Days 1 and 15 of each cycle. On Day 1, chlorambucil will be given as soon as the subject comes into clinic. Pre-medications and obinutuzumab will then be given as outlined below. Chlorambucil will be administered in the clinic on days which coincide with concomitant obinutuzumab (Days 1 + 15 of Cycle 1 and Day 1 of Cycles 2-6) and will be issued to the subject for home administration on other occasions (Day 15 of Cycles 2-6).

For subjects who have difficulty taking the entire dose of chlorambucil at a single time, the pills may be split up into 2 to 3 batches to be taken over 8 hours on the same day. The dose should not be taken over more than one day.

**Obinutuzumab** will be administered intravenously at a fixed dose of 1000 mg over 6 cycles: given on Days 1+2 (100 mg on Day 1 and 900 mg on Day 2), 8 and 15 of Cycle 1 and on Day 1 only of subsequent cycles.

Intravenous obinutuzumab will be administered per Section 5.3.2.3.

In the event of permanent discontinuation of concomitant obinutuzumab therapy, treatment with chlorambucil will continue as originally scheduled.

## **5.3. Study Medications**

### **5.3.1. Ibrutinib**

#### **5.3.1.1. Formulation/Packaging/Storage**

Ibrutinib capsules are provided as a hard gelatin capsule containing 140 mg of ibrutinib. All formulation excipients are compendial and are commonly used in oral formulations. Refer to the ibrutinib IB for a list of excipients.

The ibrutinib capsules will be packaged in opaque high-density polyethylene plastic bottles with labels bearing the appropriate label text as required by governing regulatory agencies. All study drug will be dispensed in child-resistant packaging.

Refer to the pharmacy manual/site investigational product manual for additional guidance on study drug storage, preparation and handling.

Study drug labels will contain information to meet the applicable regulatory requirements.

### **5.3.1.2. Dose and Administration**

Ibrutinib 420 mg (3 x 140-mg capsules) is administered orally once daily. The capsules are to be taken around the same time each day with 8 ounces (approximately 240 mL) of water. The capsules should be swallowed intact and subjects should not attempt to open capsules or dissolve them in water. The use of strong CYP3A inhibitors/inducers, and grapefruit and Seville oranges should be avoided for the duration of the study (Appendix C).

If a dose is not taken at the scheduled time, it can be taken as soon as possible on the same day with a return to the normal schedule the following day. The subject should not take extra capsules to make up the missed dose.

The first dose will be delivered in the clinic on Day 1, after which subsequent dosing is typically on an outpatient basis. Ibrutinib will be dispensed to subjects in bottles at each visit. Unused ibrutinib dispensed during previous visits must be returned to the site and drug accountability records (Section 12.8) updated at each visit. Returned capsules must not be re-dispensed to anyone.

### **5.3.1.3. Overdose**

Any dose of study drug administered in excess of that specified in this protocol is considered to be an overdose. Signs and symptoms of an overdose that meet any Serious Adverse Event (SAE) criterion must be reported as a SAE in the appropriate time frame and documented as clinical sequelae to an overdose.

There is no specific experience in the management of ibrutinib overdose in patients. No maximum tolerated dose (MTD) was reached in the Phase 1 study in which subjects received up to 12.5 mg/kg/day (1400 mg/day). Healthy subjects were exposed up to single dose of 1680 mg. One healthy subject experienced reversible Grade 4 hepatic enzyme increases (AST and ALT) after a dose of 1680 mg. Subjects who ingested more than the recommended dosage should be closely monitored and given appropriate supportive treatment.

Refer to Section 11.4 for further information regarding AE reporting.

### **5.3.1.4. Dose Modification for Adverse Reactions**

Treatment with ibrutinib should be held for any unmanageable, potentially study drug-related toxicity that is Grade 3 or higher in severity.

A hematologic AE grading scheme for hematologic toxicity is included in Appendix D.

The dose of study drug must be modified according to the dose modification guidance in Table 1 if any of the following toxicities occur:

- Grade 4 neutropenia (ANC<500/ $\mu$ L) for more than 7 days. See Section 6.1 for instructions regarding the use of growth factor support.
- Grade 3 thrombocytopenia (platelets<50,000/ $\mu$ L) in the presence of clinically significant bleeding events.
- Grade 4 thrombocytopenia (platelets<25,000/ $\mu$ L).
- Grade 3 or 4 nausea, vomiting, or diarrhea if persistent, despite optimal anti-emetic and/or anti-diarrheal therapy.
- Any other Grade 4 or unmanageable Grade 3 toxicity.

A high number of circulating malignant cells (>400,000/ $\mu$ L) may confer increased risk; these subjects should be closely monitored. Administer supportive care such as hydration and/or leukopheresis as indicated. Ibrutinib may be temporarily held, and medical monitor should be contacted.

**Table 1: Ibrutinib Dose Modifications**

Occurrence	Action to be Taken
First	Withhold study drug until recovery to Grade $\leq$ 1 or baseline; may restart at original dose level
Second	Withhold study drug until recovery to Grade $\leq$ 1 or baseline; may restart at 1 dose level lower (ie, 280 mg/day for 420 mg/day dose)
Third	Withhold study drug until recovery to Grade $\leq$ 1 or baseline; may restart at 1 dose level lower (ie, 140 mg/day for 420 mg/day dose)
Fourth	Discontinue study drug

Study treatment interruptions, dose reductions or modifications, or any other changes in study drug administration should be recorded in the clinical database. Study treatment should be discontinued in the event of an ibrutinib toxicity lasting more than 28 days, unless reviewed and approved by the Medical Monitor. Note: Temporary withholding of study drug for as little as 7 days can cause a transient worsening of disease and/or of constitutional symptoms. Study drug should be re-started as soon as clinically appropriate.

After a dose reduction, dose escalations of ibrutinib to the previous higher dose may be considered after consultation with the Medical Monitor if the event does not recur after at least one cycle of the lower dose.

For required dose modification for hepatic impairment refer to Section 5.3.1.6 and for concomitant treatment with CYP3A inhibitors refer to Section 6.2.1.

#### 5.3.1.5. Leukocytosis/Leukostasis

A high number of circulating malignant cells (>400,000/ $\mu$ L) may confer increased risk of leukostasis; these subjects should be closely monitored. Administer supportive care such as

hydration and/or leukophoresis as indicated. Ibrutinib may be temporarily held, and medical monitor should be contacted.

#### **5.3.1.6. Dose Modification for Hepatic Impaired Subjects**

Ibrutinib is metabolized in the liver and therefore subjects with clinically significant hepatic impairment at the time of Screening (Child- Pugh class B or C) are excluded from study participation. For subjects who develop mild liver impairment while on study (Child-Pugh class A), the recommended dose reduction for ibrutinib/placebo is to a level of 280 mg daily (two capsules). For subjects who develop moderate liver impairment while on study (Child-Pugh class B), the recommended dose reduction is to a level of 140 mg daily (one capsule). Subjects who develop severe hepatic impairment (Child-Pugh class C) must hold study drug until resolved to moderate impairment (Child-Pugh class B) or better. Monitor subjects for signs of toxicity and follow dose modification guidance as needed (Refer to Appendix J).

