
Inclusion Criteria:
 
Refer to Section 4 for the complete and detailed list of inclusion/exclusion criteria.
	
Disease Related
 
 
1. Diagnosis of CLL/SLL that meets IWCLL diagnostic criteria (Hallek 2008)
 
2. Age 65 yrs and older OR if less than 65 years old, must have at least one of the following criteria: 
 
a) Cumulative Illness Rating Score (CIRS) >6
 
b) Creatinine clearance <70 mL/min using the Cockcroft-Gault equation
 
c) Del 17p by FISH or TP53 mutation by PCR or Next Generation Sequencing (NGS)
 
 
 
3. Active disease meeting at least 1 of the following IWCLL criteria (Hallek 2008) for requiring treatment: 
 
a) Evidence of progressive marrow failure as manifested by the development of, or worsening of, anemia and/or thrombocytopenia
 
b) Massive, progressive, or symptomatic splenomegaly
 
c) Massive nodes or progressive or symptomatic lymphadenopathy
 
d) Progressive lymphocytosis
 
 
 

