##### **7.1.1.2. Confirm Eligibility**

All necessary procedures and evaluations must be performed to document that the subject meets all of the inclusion criteria and none of the exclusion criteria prior to randomization (Section 4).

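### Child-Pugh class B or C at Screening is excluded in Section 5.3.1.6 but is missing from the Section 4 and synopsis eligibility lists

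*Protocol*

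**What the plan says.** Protocol Section 5.3.1.6 opens its guidance on hepatic impairment with an eligibility rule: "subjects with clinically significant hepatic impairment at the time of Screening (Child- Pugh class B or C) are excluded from study participation". It then covers impairment that arises on study: reduce to 280 mg for class A, reduce to 140 mg for class B, and hold for class C until class B or better.

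Eligibility is confirmed elsewhere. Section 7.1.1.2 requires the procedures needed to "document that the subject meets all of the inclusion criteria and none of the exclusion criteria prior to randomization (Section 4"). The synopsis describes that section in the same way: "Refer to Section 4 for the complete and detailed list of inclusion/exclusion criteria". Section 4.2 introduces its 21 items by saying that "potential subjects must meet NONE of the following exclusion criteria". Neither the 12 inclusion criteria in Section 4.1, nor the 21 exclusions, nor the synopsis lists contain a Child-Pugh criterion.

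The liver-function requirement in Section 4.1 is inclusion 6, headed "Adequate hepatic and renal function defined as". For the liver it sets AST or ALT at no more than 2.5 x ULN and bilirubin at no more than 1.5 x ULN, with exceptions for Gilbert's syndrome and non-hepatic causes.

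**The concern.** The list that sites are told to use, and that the synopsis calls complete, lacks an exclusion that the protocol states flatly in a dosing section. A site that confirms eligibility exactly as directed could admit a subject whom Section 5.3.1.6 bars. That subject would be eligible under one part of the protocol and ineligible under another, so it would be unclear whether enrolment was a deviation.

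The stake is drug exposure. Section 1.2.2.1 reports that, after a single dose, ibrutinib AUC was 8.2-fold (class B) and 9.8-fold (class C) that of subjects with normal liver function. The dose reductions in Section 5.3.1.6 are written for impairment that develops on study, so a subject enrolled with class B has no stated starting dose other than the standard 420 mg.

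**Working it through.** The plan gives no figure to reproduce here. The check is whether anything in Section 4 has the same effect as the Section 5.3.1.6 exclusion.

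**Step 1. Does inclusion 6 imply class A?** Appendix J scores five items from 1 to 3 points each, in the order bilirubin + albumin + PT/INR + ascites + encephalopathy. Class A is 5-6 points, B is 7-9 and C is 10-15. Inclusion 6 limits only the first of these items (together with AST/ALT, which Child-Pugh does not use).

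Take a subject with liver disease whose bilirubin is below both 2 mg/dL and 1.5 x ULN. Bilirubin then scores 1 point and meets inclusion 6, and no value for ULN need be assumed. With AST or ALT within the limit:

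| Findings (all other items at 1 point) | Points | Class |
|---|---|---|
| Albumin 28-35 g/L and mild ascites | 1+2+1+2+1 = 7 | B |
| Albumin 28-35 g/L and PT/INR 1.71-2.30 | 1+2+2+1+1 = 7 | B |
| PT/INR 1.71-2.30 and mild ascites | 1+1+2+2+1 = 7 | B |
| All three of these | 1+2+2+2+1 = 8 | B |
| Albumin below 28 g/L alone | 1+3+1+1+1 = 7 | B |
| Albumin below 28 g/L, PT/INR 1.71-2.30, moderate to severe ascites | 1+3+2+3+1 = 10 | C |

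With bilirubin at 1 point, the other four items have 3 x 3 x 3 x 3 = 81 score patterns: 5 are class A, 45 class B and 31 class C. This shows only that inclusion 6 does not confine subjects to class A. It counts score patterns and says nothing about how common such subjects are.

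**Step 2. Does another Section 4 item close the gap?** Three come near, and each removes only some of these subjects:

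- Exclusion 12 deals with active hepatitis B or C ("Those who are PCR positive will be excluded"). It does not reach liver disease from other causes.
- Exclusion 14 ("Any life-threatening illness, medical condition, or organ system dysfunction that") applies only if, in the investigator's opinion, safety or the study outcomes are at risk. The rule in Section 5.3.1.6 is categorical.
- Inclusion 10 ("Ability to provide written informed consent and to understand and comply with the requirements of the study") and exclusion 21 would remove a subject whose encephalopathy prevents understanding or consent. They would not remove the subjects in the table, who score 1 point for encephalopathy.

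**Step 3. Does a Screening step produce the score?** The Screening list in Section 8.1.1 and the schedule in Appendix A both include CIRS. Neither includes a Child-Pugh score.

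**Step 4. Size.**

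- Dose ratio for a class B subject enrolled in Arm A: 420 / 140 = 3.
- Subjects allocated to start ibrutinib at 1:1: 212 / 2 = 106 of those planned, or 229 / 2 = 114.5 of the number randomized given in Section 10.7.2.3. This is the size of Arm A, not the number at risk.
- The documents do not give the number of class B or C subjects.

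**The case against.** The strongest reply is that this is a matter of placement. No Section 4 item admits a class B or C subject, so Section 4 and Section 5.3.1.6 can both be followed, and Section 12.10 binds the investigator to the whole protocol. That stands in part: the rule is binding and is misplaced rather than absent. It does not rescue a list that is described as complete and is the only one named for confirming eligibility.

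Other safeguards can be cited. The text under Table 1 in Section 5.3.1.4 sends readers to Section 5.3.1.6, CIRS has a hepatic/biliary item, and Screening includes abdominal examination, CT, albumin and PT/INR. These make an error less likely. However, the pointer in Section 5.3.1.4 is for dose modification, which comes after randomization. CIRS has no upper limit for entry and no threshold on its hepatic item. The laboratory and examination findings are collected but not combined into the score the exclusion needs.

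It can also be said that no starting dose is needed for subjects who are excluded, and that 420 mg would be given only contrary to Section 5.3.1.6. This is correct if that sentence governs. The threefold ratio describes the result of an enrolment error, not a dose the protocol intends for such a subject.

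Finally, Section 10.7.2.3 bases the OS power on 229 randomized subjects against about 212 planned, which suggests that enrolment was complete by this version. If so, no further enrolment decision would change. This is an inference, and the text would still be inconsistent.

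**Conclusion.** The concern holds as a minor internal inconsistency. It is certain that Section 5.3.1.6 states an exclusion that Section 4 and the synopsis omit, and that the stated eligibility procedure can admit a class B subject. That conclusion rests only on the protocol text and the Appendix J scoring.

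Which side was intended is not settled. Section 5.3.1.6 also refers to a placebo, although Section 5.1 describes an open-label trial with no blinding. This hints that the text was carried over from another protocol, but that is inference only.

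The practical effect is probably small. The exposure concern at randomization is confined to Arm A, few subjects are likely to have class B or C disease, and the AUC figures describe single-dose exposure, not demonstrated harm. No endpoint, power figure, analysis population or analysis method is affected.

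**What to change.** If the exclusion is intended, add Child-Pugh class B or C hepatic impairment at Screening, with a reference to Appendix J, to Section 4.2 and to the synopsis exclusions. Add a step to Section 8.1.1 and Appendix A to derive the score at Screening for subjects with liver impairment.

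If the sentence in Section 5.3.1.6 was carried over and such subjects were meant to be eligible, correct that section instead and state their starting dose there.

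The cost of the first option is one line in Section 4.2, one in the synopsis, and one scoring step. No new test is needed: albumin and bilirubin (Section 7.1.2.2), PT/INR (Section 7.1.2.3) and the abdominal and nervous-system examination (Section 7.1.1.6) are already collected at Screening.

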### 1.2.2.1. Pharmacokinetics and Product Metabolism

Following oral administration of ibrutinib at doses ranging from 420 to 840 mg/day, exposure to ibrutinib increased proportionally to doses increased with substantial intersubject variability. The mean half-life ( $t_{1/2}$ ) of ibrutinib ranged from 4 to 13 hours, with a median time to maximum plasma concentration ( $T_{max}$ ) of 2 hours.

Taking into account the approximate doubling in mean systemic exposure when dosed with food and the favorable safety profile, ibrutinib can be dosed with or without food. Ibrutinib is extensively metabolized primarily by cytochrome P450 (CYP) 3A4. The on-target effects of metabolite PCI-45227 are not considered clinically relevant. Steady-state exposure of ibrutinib and PCI-45227 was less than 2-fold of first dose exposure. Less than 1% of ibrutinib is excreted renally. Ibrutinib exposure is not altered in patients with creatinine clearance (CrCl) >30 mL/min. Patients with severe renal impairment or patients on dialysis have not been studied. Following single dose administration, the AUC of ibrutinib increased 2.7-, 8.2- and 9.8-fold in subjects with mild (Child-Pugh class A), moderate (Child-Pugh class B), and severe (Child-Pugh class C) hepatic impairment compared to subjects with normal liver function. A higher proportion of Grade 3 or higher adverse reactions were reported in patients with B-cell malignancies (CLL, MCL and WM) with mild hepatic impairment based on NCI organ dysfunction working group (NCI-ODWG) criteria for hepatic dysfunction compared to patients with normal hepatic function.

For the most comprehensive information regarding pharmacokinetics (PK) and product metabolism, please refer to the current version of the ibrutinib IB.

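### Mild (Child-Pugh class A) hepatic impairment already present at Screening starts ibrutinib at 420 mg, while the same impairment arising on study is reduced to 280 mg, with no reason given

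*Protocol*

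**What the plan says.** **Hepatic rule.** Protocol Section 5.3.1.6 states that "subjects with clinically significant hepatic impairment at the time of Screening (Child- Pugh class B or C) are excluded from study participation". Class A is not excluded. For impairment that arises later, "For subjects who develop mild liver impairment while on study (Child-Pugh class A), the recommended dose reduction for ibrutinib/placebo" is to 280 mg a day. Class B arising on study goes to 140 mg, and class C means a hold until recovery to class B or better. (The trial has no placebo; nothing turns on that word.) Section 5.3.1.6 words the reductions as recommended, while the text after Table 1 in Section 5.3.1.4 refers to them as required.

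**Starting dose.** Section 5.3.1.2 says "Ibrutinib 420 mg (3 x 140-mg capsules) is administered orally once daily". Section 5.2.1 gives the same dose for Arm A. Neither makes an exception for the liver.

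**Eligibility.** Section 7.1.1.2 has eligibility checked against Section 4. Inclusion criterion 6 ("Adequate hepatic and renal function defined as") limits AST or ALT to 2.5 x ULN and bilirubin to 1.5 x ULN, the latter waived for Gilbert's syndrome or a non-hepatic cause. Section 4 contains no Child-Pugh, albumin, INR or ascites criterion.

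**Exposure.** Section 1.2.2.1 reports that after a single dose "the AUC of ibrutinib increased 2.7-, 8.2- and 9.8-fold in subjects with mild (Child-Pugh class A), moderate (Child-Pugh class B), and severe" (class C) "hepatic impairment compared to subjects with normal liver function". It also reports more Grade 3 or higher reactions in mild impairment, graded there on a different scale (NCI-ODWG).

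**Next-line ibrutinib.** Under Section 8.4, Arm B subjects who progress can receive ibrutinib on the Appendix I schedule. That table marks hematology at the assessment visit, at every treatment visit and at end of treatment, but serum chemistry only at the assessment visit.

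**The concern.** The 280 mg step exists because an impaired liver raises ibrutinib exposure. Both the reason given in Section 5.3.1.6 (hepatic metabolism) and the AUC figures in Section 1.2.2.1 concern the state of the liver, not the date on which it began. The protocol's other exposure-based rule, for CYP3A inhibitors in Section 6.2.1, works that way: the dose is reduced for as long as the inhibitor is in use.

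The hepatic rule instead depends on onset. Followed as written, a subject who enters with diagnosed mild impairment takes 420 mg and never meets the 280 mg trigger. The next hepatic step that applies is the 140 mg one, on worsening to class B. At stake is avoidable over-exposure in a group for which the sponsor has already judged 280 mg suitable.

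The Appendix I gap bears on the same rule. Section 5.3.1.6 is not limited to Arm A, yet bilirubin and albumin, two of the five Child-Pugh items, have no scheduled value once next-line treatment has begun.

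**Working it through.** There is no plan figure to reproduce. The check sets the sections side by side and scales the exposure that the protocol reports.

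**1. Can a subject with class A impairment enter?** Appendix J scores five items at 1 to 3 points each; class A is 5-6 points.
- Bilirubin will rarely supply the sixth point. If ULN is 1.2 mg/dL (my assumption), the entry limit is 1.5 x 1.2 = 1.8 mg/dL, below the 2 mg/dL at which a second point starts. The two meet at a ULN of 2/1.5 = 1.33 mg/dL.
- Albumin can supply it. A value of 28-35 g/L scores 2 points, so the total is 2 + 4 x 1 = 6, which is class A. Albumin is not an entry criterion, so such a subject with liver disease can meet every Section 4 laboratory limit.

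Entry is therefore possible, unless the investigator applies exclusion 14 (organ dysfunction judged to compromise safety).

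**2. Dose by time of onset.**

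| Hepatic state | Present at Screening | Arises on study |
|---|---|---|
| Mild (class A) | 420 mg (5.2.1, 5.3.1.2; no exception) | 280 mg (5.3.1.6) |
| Moderate (class B) | excluded | 140 mg |
| Severe (class C) | excluded | hold |

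Dose ratio for class A: 420/280 = 1.5.

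**3. Exposure relative to a normal liver on 420 mg.** Formula: AUC ratio x dose/420, with the AUC ratio of 2.7 from Section 1.2.2.1.
- Class A at 420 mg: 2.7 x 420/420 = 2.7.
- Class A at 280 mg: 2.7 x 280/420 = 1.8.

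Section 1.2.2.1 states dose proportionality for 420 to 840 mg only, so extending it down to 280 mg is an assumption. If exposure fell less than proportionally, the 280 mg figure would lie between 1.8 and 2.7.

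**4. Number of subjects.** Not in the documents. For scale only, planned Arm A is 212/2 = 106. An assumed 1% to 5% gives 106 x 0.01 = 1.1 to 106 x 0.05 = 5.3, or about 1 to 5 subjects.

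**5. Child-Pugh items with a scheduled on-treatment source.**
- Main schedule: bilirubin and albumin (serum chemistry), ascites and encephalopathy (physical examination) = 4 of 5. PT/INR is at Screening only (Section 7.1.2.3, Appendix A).
- Appendix I: ascites and encephalopathy = 2 of 5. Bilirubin, albumin and INR are missing.

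**6. Does the INR matter?** It can. If the other four items total 4, an INR score of 1, 2 or 3 gives class A, A or B. If they total 5, it gives A, B or B. That boundary separates 280 mg from 140 mg.

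**The case against.** The 420 mg start is inferred from silence: no sentence says that class A impairment at entry takes the full dose. Stable mild impairment at entry and impairment newly arising on the drug may also be different clinical situations. Both remarks are fair. But Sections 5.2.1 and 5.3.1.2 set one dose with no exception, and the protocol does not argue that the two situations differ.

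Safeguards exist. Exclusion 14 is available, Section 5.3.1.6 asks for toxicity monitoring, and Section 5.3.1.4 provides dose holds. These stand, but exclusion 14 is discretionary and sets no dose. The holds act only after toxicity, and Table 1 allows a restart at the original dose after a first occurrence.

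The harm may be small. Section 5.3.1.3 reports no maximum tolerated dose up to 1400 mg/day, which is 1400/420 = 3.3 times the trial dose. Section 1.2.2.1 accepts roughly doubled exposure with food. The Grade 3 signal uses another scale, and the 2.7-fold figure is from single doses. This argues for low severity, and I accept it. It does not explain why the same grade of impairment warrants 280 mg in one case and 420 mg in the other.

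A reader might infer two stronger points, which the documents do not support.
- *Class A cannot mark onset, because a normal liver scores 5 and is also class A.* The arithmetic is right, but the trigger in Section 5.3.1.6 is the development of liver impairment, and class A is only its grade. Appendix J is titled for subjects with liver impairment, and Section 1.2.2.1 separates class A impairment from normal liver function.
- *Child-Pugh cannot be scored on study, because PT/INR is scheduled only at Screening.* Section 8.2 lets local laboratories guide dosing decisions, so an investigator who suspects impairment can order an INR. What remains is a note that one should be obtained.

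**Conclusion.** The inconsistency is real and narrow. Diagnosed mild (class A) impairment at Screening is admissible and starts ibrutinib at 420 mg; the same grade arising on study goes to 280 mg; no reason is given. The size is a 1.5-fold dose difference, or 2.7-fold against 1.8-fold exposure relative to a normal liver on 420 mg. The exposure figures rest on the single-dose AUC ratio and on dose proportionality below 420 mg, which the protocol does not state. The number affected is unknown and probably small.

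The Appendix I gap also holds: as printed, bilirubin and albumin have no scheduled value during next-line treatment. Section 8.2's allowance for local laboratories lets an investigator order them but does not schedule them.

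This is a cheap improvement to safety dosing. Nobody should read into it an effect on PFS, alpha or power; the affected group is too ill-defined in the documents to support such a claim, and the sample size and testing plan do not depend on the hepatic rule.

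**What to change.** - In Sections 5.2.1 and 5.3.1.6, state that subjects with diagnosed mild hepatic impairment (Child-Pugh class A) at Screening start ibrutinib at 280 mg, in line with the on-study rule.
- In Appendix I, add serum chemistry at the treatment visits where hematology is already drawn, so that the hepatic dose rule can be applied to next-line subjects.
- As a note in Section 5.3.1.6, ask for PT/INR when hepatic impairment is suspected.

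The cost is a few sentences, one added assay on blood draws that already take place, and an occasional INR. The downside is a lower starting dose in a probably small group whose number the documents do not give. The sponsor already accepts that dose for the same grade of impairment when it arises on study.
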